#### 3 PROGRAMME DESIGN

The SleepAD programme is comprised of two sub-studies which will run in parallel utilising distinct but potentially overlapping participants.

#### Sub-Study 1

Design: Single centre, prospective observational feasibility study with longitudinal follow up.

SleepAD Protocol v6.0 6th September 2024

Setting: Southmead Hospital cognitive disorders clinic and participants' homes.

### Sub-Study 2

Design: Single centre, prospective observational feasibility and diagnostic accuracy study with longitudinal follow up.

Setting: Southmead Hospital cognitive disorders clinic.

#### **4 STUDY POPULATION**

#### 4.1 Method Of Recruitment

#### Sub-Study 1

Target population and inclusion/exclusion criteria: The primary method of recruitment will be to approach participants who fulfil the criteria of Mild Cognitive Impairment (MCI) or early dementia due to Alzheimer's Disease (AD) [51] in the ARUK funded DOPAMIND 2 trial (set to begin recruitment November 2022) and the Above and Beyond Funded RESTED study (recruiting from November 2021). Both studies are run by our research group and participants have consented to being approached about other research opportunities.

If we do not meet the sample size from these two studies, participants will be identified by the research team through one of six sources:

- 1. The North Bristol NHS Trust Cognitive Disorders Clinic (led by EC) which receives approximately 20-25 referrals on a weekly basis.
- 2. The North Bristol NHS Trust Mild Cognitive Impairment Clinic / Brain Health Clinic which currently holds a caseload of approximately 80.
- 3. Memory Clinic Database A confidential and secure database maintained by the ReMemBr group in North Bristol NHS Trust for the purposes of undertaking medical research and statistical analysis currently holding approximately 1600 records. This contains contact details for current and previous CDC or MCI clinic attendees, a proportion of whom have previously expressed an interest in future research participation.
- 4. In addition we will recruit through the Join Dementia Research (JDR) national research register for local people interested in taking part. If clinical research network portfolio status is granted, we will recruit with support of local clinical research network staff where appropriate.
- 5. Participants in other research studies (beyond those already stated above) run at the Bristol Brain Centre, who meet eligibility criteria.
- 6. Members of the public who have approached the Brain Centre expressing interest in research participation.

We plan to recruit through primary care and from public spaces using posters and leaflets where we may reach potential participants e.g. hospital and GP waiting rooms. We will advertise this study on our website at www.remembrgroup.com and possibly on other websites.

We will also be using 'Join dementia research' (JDR) as a recruitment tool. This is an online self-registration service that enables volunteers with memory problems or dementia, carers of those with memory problems or dementia and healthy volunteers to register their interest in

SleepAD Protocol v6.0 6th September 2024

taking part in research. The purpose of JDR is to allow such volunteers to be identified by researchers as potentially eligible for their studies. Researchers can then contact volunteers, in line with the volunteers' preferred method of contact, to further discuss potential inclusion. JDR is funded by Department of Health working in partnership with the charities Alzheimer Scotland, Alzheimer's Research UK and Alzheimer's Society and is Health Research Authority (HRA) endorsed. The online service and all associated documentation, methods of contacting volunteers and handling of data, were reviewed by a specially convened HRA committee which included experts in research ethics, data protection and information governance. Formal endorsement was issued by the HRA in a letter dated 20 May 2014.

### Sub-Study 2

Target population and inclusion/exclusion criteria: we will approach every person in whom we are performing LP for Alzheimer's biomarkers. We use CSF testing in patients with early disease or in whom the diagnosis is not clear and where Alzheimer's disease is a possibility and many of these patients will also take part in objective 1.

#### 4.2 Inclusion Criteria

### For Sub-Study 1

- 1. Age > 50
- 2. All participants must express that they are willing to take part in this study and adhere to the study procedures
- 3. Full capacity to consent to involvement
- 4. Clinical diagnosis of MCI due to AD[52] or mild AD[51] according to standardised criteria

(NB people with a mixed AD/Vascular dementia diagnosis are eligible for inclusion)

### For Sub-Study 2

- 1. All participants undergoing CSF testing clinically including CSF biomarkers of AD.
- 2. All participants must express that they are willing to take part in this study and adhere to the study procedures.
- 3. Full capacity to consent to involvement

#### 4.3 Exclusion Criteria

#### For Sub-Study 1

- 1. Severe medical or psychiatric co-morbidity, which, in the opinion of the investigator, may substantially impact on sleep.
- 2. Clinically significant sleep disorder as defined by ICD-10 or equivalent pre-dating and / or not related to AD pathology.
- 3. Diagnosis of dementia other than AD.
- 4. Montreal Cognitive Assessment (MoCA) < 11/30, except where the MoCA is not considered to be an accurate reflection of clinical presentation (e.g., in the case of prominent speech disorder) in the opinion of the investigator.

SleepAD Protocol v6.0 6th September 2024

#### For Sub-Study 2

1. Severe medical or psychiatric co-morbidity, which, in the opinion of the investigator, may substantially impact on the ability to tolerate withdrawal of an extra 10ml of blood.

### 4.4 Participant Numbers

### For Sub-Study 1

Sample Size: of 50 allows key feasibility parameters to be estimated with a suitable level of precision

### For Sub-Study 2

Sample Size: of 100 will allow key feasibility and diagnostic accuracy parameters to be estimated with a suitable level of precision e.g. a marginal error of 0.08 assuming an AUROC of 0.9 and 50% prevalence in binary classification of AD | not AD.

#### 5 PARTICIPANT SELECTION AND ENROLMENT

### 5.1 Pre-screening potential participants

### For Sub-Study 1

All prospective participants will first be contacted by telephone (or face to face if consultation planned) by a member of the clinical team to establish whether they are potentially interested in participating, and if so, details will be passed to a member of the research team.

A member of the research team will then make contact by phone to provide an outline of the study and will ask about their general health. This is in order to rule out participants who have medical diagnoses or problems that may prevent them from taking part in this study, such as a severe medical co-morbidity interfering with sleep. Another goal of the pre-screening phone call is to schedule the first screening consultation. We will give the potential participant as much time as they need to decide whether they wish to undergo the first screening consultation.

If the prospective participant does not already possess a copy of the Patient Information Sheet (PIS), this will be sent by post or electronically. Prospective participants with a carer are invited to bring this person along with them for the screening consultation.

#### For Sub-Study 2

Clinicians will consider eligibility for the study at the point of booking patients in for a routine lumbar puncture in the Brain Centre clinic, and if the prospective participant is interested they will be signposted to the research team. A member of the research team will then make contact by phone to discuss the study, and if appropriate to gain verbal consent to participate.

SleepAD Protocol v6.0 6th September 2024

For participants with speech or communication difficulties, a face-to-face appointment will be offered instead of a phone call.

During the subsequent lumbar puncture appointment, consent will be confirmed in writing by a GCP trained member of the team.

## 5.2 Screening Consultation

### For Sub-Study 1

Screening consultations can be conducted in-person or remotely.

Each potential participant will be reviewed by an International Conference on Harmonisation Good Clinical Practice (ICH GCP) trained member of the study team. Participants will first be given a detailed explanation of the study, orally as well as another copy of the PIS if they wish. The research team will check understanding of the PIS and an opportunity to ask questions will be provided. If they agree to take part in the study each participant will sign an Informed Consent Form (ICF). Participants scheduled for remote consultation will have received a copy of the PIS and ICF via post and will be asked to return a signed copy to the research team. Capacity to consent is assessed as explained in Section 5.3.

Each prospective participant will subsequently be reviewed against inclusion / exclusion criteria before final eligibility is determined.

The participant will subsequently undergo medical screening (see Section 6.1) before undergoing baseline assessments (see Section 6.2) if eligible.

Any participant unsure or requiring more time to make a decision as regards to consent will be offered this opportunity and given as much time as they need, providing recruitment is ongoing.

Substudy 2 - no screening visit

### 5.3 Consenting Participants

Anyone taking part will be informed of the study aims and protocol. It will be made clear to participants that if they wish to, they may withdraw their consent at any time without the need to provide an explanation and that this will not affect future medical care.

The investigator taking consent will be trained in taking consent and will act in accordance with GCP. Capacity to consent is assessed by the researcher as they discuss the information sheet with the patient. The researchers will ensure the volunteer has understood and retained information for long enough to allow risks and benefits to be considered and that a decision can be relayed clearly.

Substudy 1 only Once the volunteer has given consent, they will perform the Montreal Cognitive Assessment (MoCA). This is a widely used assessment for measuring cognitive ability within clinical and research settings. If a participant scores below 11/30 they will be withdrawn from this study as this is highly likely to be associated with a reduced capability to

SleepAD Protocol v6.0 6th September 2024

provide informed consent and adhere to study procedures. However, if the MoCA is not considered to be an accurate reflection of clinical presentation (e.g., in the case of prominent speech disorder) in the opinion of the investigator, then inclusion would still be considered on a case-by-case basis.

#### 5.4 Carer Involvement

We will encourage all prospective patients with MCI/AD to be accompanied with a carer for the screening consultation if they wish.

### 5.5 Withdrawal of Participation

Participants are free to withdraw from the study and to opt-out at any point or a participant can be withdrawn by the Investigator. If withdrawal occurs, the participant will have the option as to whether they wish to allow previously collected data to be utilised for ongoing research. The reason for withdrawal will be documented in the participant's case report form (CRF) although a reason would not have to be provided.

#### 6 STUDY ASSESSMENTS

### 6.1 Screening Assessments

### For Substudy 1

The following information will be gathered during the initial screening assessment:-

- Medical History and Current Diagnoses
   Specifically to determine the presence of severe medical comorbidities likely to impact
   on sleep or the presence of a primary sleep disorder unrelated to a neurodegenerative
   cause
- Previous Investigation Results
   Including neuroimaging data, CSF biomarker results and neuropsychometry data;
   information historically collected as part of routine clinical care.
- Medication History
- Physical Observations\*
   Blood pressure measurement only

#### 6.2 Baseline Assessments

#### For Substudy 1

The following assessments will occur following informed consent during the initial consultation. These are validated questionnaires and post hoc analysis will allow us to probe whether any of these questionnaires can help stratify in which patients home EEG will be feasible for future trials.

#### Cognitive Assessments

SleepAD Protocol v6.0 6th September 2024

\* If undergoing face-to-face consultation

Montreal Cognitive Assessment (MoCA) [24]

### Sleep Assessments

- Pittsburgh Sleep Quality Index (PSQI)[53]
- Epworth Sleepiness Scale (ESS) [54]
- STOP-BANG (OSA Screening Questionnaire)[55]
- Ultra-Short Munich Chronotype Questionnaire (µ-MCTQ)[56]
- REM Sleep Behavioural Disorder Single Screening Question[57]

Blood biomarkers - Venepuncture of 5-10 ml blood biomarkers taken for analysis of biomarkers (P-tau & NFL, GFAP and abeta42/40, and possibly others in future)

### Other Assessments

- Restless Leg Syndrome Single Screening Questionnaire [58]
- Generalised Anxiety Disorder 7 Questionnaire (GAD-7)[59]
- Geriatric Depression Scale Short Form (GDS-15) [60]
- Apathy Evaluation Scale Self-Rated (AES-S) [61]
- SleepAD sleep questionnaire (see appendix)

The study team will also record basic demographic information (e.g. age, sex, ethnic group, occupation, employment status).

### 6.3 Main Study Assessments

#### For Substudy 1

- Venepuncture of 5-10 ml blood biomarkers taken for analysis of biomarkers (P-tau & NFL, GFAP and abeta42/40, and possibly others in future). The blood sample will either be arranged to be taken during a routine clinical appointment venepuncture at the Brain Centre (i.e. not an extra venepuncture), or during a separate appointment (which would require a new venepuncture).
- Sleep recording participants will undergo EEG recording at home for 3 nights and will also complete a Consensus Sleep Diary questionnaire [62] each night. The sleep monitoring will be performed using high-density at-home EEG equipment which will be set up by the researcher in the participant's home. This will involve participants undergoing full polysomnography (PSG), where electrophysiological data from electrodes placed on the scalp, face and body will be recorded. The home setup is designed to closely replicate the setup used in sleep laboratories. Participants will wear a 32-channel sleep cap including scalp and auxiliary channel location using a wireless LiveAmp 32-channel active electrode system (Brain Products UK). EEG recordings are acquired on an internal memory system and will subsequently be downloaded to a secure University of Bristol server. Although we do not currently have experience of sleep recordings in Alzheimer's disease, we have experience from recording sleep in patient populations of similar age, living with chronic pain. In our experience, these patients tolerate sleep recordings

SleepAD Protocol v6.0 6th September 2024

- well. Numerous EEG studies in Alzheimer's disease are reported in the literature, as reviewed elsewhere [63].
- Pulse oximetry participants will be asked to undergo two nights of overnight pulse oximetry (concurrent with EEG recording) during the 3 night window of sleep recordings. A pulse oximeter is a device routinely used in NHS practice to collect pulse oximetry data, and will be used in line with NHS protocols to monitor pulse and oxygen saturation levels and screen for obstructive sleep apnoea (OSA). Overnight pulse oximetry is an accepted and widely used screening tool for moderate to severe OSA [64]. Those with abnormal results will be offered referral to the Non-invasive Ventilation Clinic and their GP will be informed with the participant's consent.
- iv) Sleep dependent memory testing a long-term memory word test delivered by the researcher on either the second or third evening of testing (order counterbalanced)
- v) Acceptability participants will be asked to complete a brief questionnaire within 1 week of their final testing session to feedback on their experience (See appendix 2).

### For Substudy 2

Venepuncture of 5-10 ml blood biomarkers taken for analysis of biomarkers (P-tau & NFL, GFAP and abeta42/40, and possibly others in future). In all participants undergoing LP, this will be at the time when bloods are taken alongside LP in any case (i.e. there will be not an extra venepuncture, just more blood drawn). In very rare situations, for example, participants who have another form of biomarker testing (e.g. PET scanning), a new venepuncture will be needed.

As an optional addition, the collected blood sample will also be analysed for *APOE* genotype. The venepuncture already being arranged for blood biomarker analysis will provide a sufficient sample for the additional *APOE* analysis. The *APOE* analysis therefore does not require an additional blood sample/procedure.

As an optional addition, an extra < 5 ml of CSF will be taken during the routine LP for analysis and storage, as long as this does not prolong the procedure by more than 1 minute.

All patients will have had a MoCA cognitive test as part of routine care within 3 months of CSF collection. In the very rare case that this has not happened as part of routine clinical care, we will also carry out a MoCA as close as possible in time to their lumbar puncture (taking into account they might be nervous on the day of the procedure, we may do this at a different hospital visit). As an alternative, we will offer the opportunity to complete the MoCA test remotely via video call and save the need for an additional hospital visit. Several studies have demonstrated that administering the MoCA remotely via video call is a valid and reliable alternative to a face-to-face assessment.

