#### 2.1.2 Primary Objectives

### Theme 1

2.1.2.1 Feasibility of home high-density EEG (primary objective);

2.1.2.2 Acceptability of home EEG;

#### Theme 2

2.1.2.3 Feasibility of blood biomarkers for AD;

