### 2.2 Hypotheses

### 2.2.1 Primary Hypotheses:

### Theme 1

Home high-density EEG are feasible and acceptable in people with MCI and AD

### Theme 2

• Blood biomarkers are feasible and acceptable in people with MCI and AD.

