### 8.2 Frequency of Data Collection

### For substudy 1

Data will be collected during a one-off eligibility telephone conversation, an initial visit, over 3 nights of sleep EEG and then with acceptability questionnaire within 1 week of overnight testing.

Baseline data collected during the eligibility telephone conversation and initial visit will be entered by researchers into paper case report forms and then into REDCAP (electronic data capture system) or directly into REDCap. Data collected during the Study Assessment Period will comprise raw electronic data from measurement devices which will be downloaded onto secure computers at the end of the assessment period and memory test results that will be uploaded onto REDCap after testing.

#### For Substudy 2

Demographic and clinical data will be extracted from electronic medical records. Venepuncture will occur only once at the same time as clinical LP.

SleepAD Protocol v6.0 6th September 2024

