### 14.2 Quality Assurance

#### 14.2.1 Accuracy of Case Report Forms

Paper case report forms (CRFs) and electronic patient-reported outcomes (PROs) are the primary data collection instruments for the study. The Principal Investigator, or a designee will record data collected on each subject. The Principal Investigator will be responsible for the timing, completeness, legibility and accuracy of the CRF and will retain a copy of each completed form.

For paper CRFs: All data requested on the CRF will be recorded and checked by a member of the study team. All missing data will be explained. If a space on the CRF is left blank because the procedure was not done or the question was not asked, "N/D" will be inserted. If the item is not applicable to the individual case, "N/A" will be inserted. All entries will be printed legibly in ink. If any entry errors are made, to correct such an error, a single straight line will be drawn through the incorrect entry and the correct data entered above it. All such changes will be initialled and dated. Pencil and correction fluid will not be used anywhere on the CRF. If it is not clear why the change has been made, an explanation will be written next to the change. Paper CRFs will be entered into a University of Bristol approved electronic data capture system.

Each participant enrolled into the study must have the correct CRFs completed and signed by the Principal Investigator (or designee). This also applies to those participants who failed to complete the study. All data submitted on CRFs must be verifiable in the source documentation or the discrepancies explained.

SleepAD Protocol v6.0 6th September 2024

If a participant withdraws from the study during the experiment phase, the reason must be noted on the Withdrawal Form.

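### The acceptability questionnaire follows the EEG nights and is not offered to those who refuse or leave early, so a listed primary objective may rest mainly on people who tolerated the device

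*Protocol*

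**What the plan says.** The Protocol lists "2.1.2.2 Acceptability of home EEG" under the primary objectives (section 2.1.2), although the explicit primary tag is attached to feasibility. The Theme 1 primary hypothesis (section 2.2.1) is "Home high-density EEG are feasible and acceptable in people with MCI and AD".

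The instrument is the Appendix 2 experience questionnaire. On timing, section 6.3 v) says "participants will be asked to complete a brief questionnaire within 1 week of their final testing session to feedback on their experience". Section 8.2 gives the sequence for Sub-study 1 as "over 3 nights of sleep EEG and then with acceptability questionnaire within 1 week of overnight testing".

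On withdrawal, section 5.5 says "the participant will have the option as to whether they wish to allow previously collected data to be utilised for ongoing research", and also "The reason for withdrawal will be documented in the participant's case report form (CRF) although a reason would not have to be provided". Section 14.2.1 says "If a participant withdraws from the study during the experiment phase, the reason must be noted on the Withdrawal Form". On completed and signed case report forms it adds "This also applies to those participants who failed to complete the study".

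Section 11.4.1 has three further rules. Adverse effects at withdrawal are recorded. Every participant who withdraws is replaced. Data already collected are kept only if the participant agrees and the reason for leaving is unlikely to affect the data; otherwise they are disposed of unless already analysed.

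Section 10.2 b) plans to calculate acceptability ratings for home EEG.

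**The concern.** Someone who refuses the cap at set-up, or leaves the study after one night because it was uncomfortable, knows most about whether the device is acceptable. As written, the questionnaire is scheduled after the recording nights and no section extends it to these people. Section 11.4.1 then replaces them, so the planned number is reached with people who could tolerate the EEG.

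The second retention condition in section 11.4.1 adds to this. Stopping because the EEG was intolerable could be classed as a reason likely to affect the data. What had been collected could then be discarded even if the participant was content for it to be kept. Section 5.5 leaves that choice to the participant alone.

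The introduction says the programme's feasibility and acceptability data will feed directly into clinical trials. A favourable result drawn mainly from completers would make home EEG look easier to use in those trials than it is.

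**Working it through.** **1. Who is asked, reading the sections together.**

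- Completes three nights: asked (6.3 v, 8.2).
- Misses or loses a night but stays in the study: probably asked. Section 9.5 lets participants decline a repeat without affecting their participation.
- Leaves after one or two nights: unsettled. Section 6.3 v) could mean the last session attended, whereas the sequence in 8.2 puts the questionnaire after three nights. Sections 5.5 and 11.4.1 do not mention it.
- Refuses the cap at first set-up: no recording night exists from which to time the questionnaire, and no section provides for it.

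**2. What is recorded for those who leave.** A reason if they give one (5.5, 14.2.1), any adverse effect (11.4.1), and case report forms for non-completers (14.2.1). None of these is linked to the acceptability result in 10.2 b).

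**3. Size.** The Protocol states no withdrawal rate, acceptability threshold or precision figure for Sub-study 1, so there is no figure of its own to reproduce. The inputs below are assumptions, apart from the sample size.

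- w = share of those offered EEG who withdraw: 5%, 10%, 20%, 30% (assumed).
- p_c = share of completers who are favourable: 90% (assumed).
- p_w = share of withdrawers who are favourable: 0% to 50% (assumed).
- n = 50 (section 4.4) or up to 100 (section 10.1).

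Acceptability over everyone = (1 − w) × p_c + w × p_w. Overstatement when only completers answer = w × (p_c − p_w).

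| w | Started, for 50 completers: 50/(1 − w) | Acceptability over everyone | Overstatement (points) |
|---|---|---|---|
| 5% | about 53 | 85.5-88% | 0.05 × 0.40 to 0.05 × 0.90 = 2-4.5 |
| 10% | about 56 | 81-86% | 0.10 × 0.40 to 0.10 × 0.90 = 4-9 |
| 20% | about 63 | 72-82% | 0.20 × 0.40 to 0.20 × 0.90 = 8-18 |
| 30% | about 71 | 63-78% | 0.30 × 0.40 to 0.30 × 0.90 = 12-27 |

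**4. Against sampling error.** The 95% half-width for a proportion is 1.96 × √(p(1 − p)/n). At p = 0.9 it is 1.96 × √(0.09/50) = 8.3 points for n = 50, and 5.9 points for n = 100. At 10-20% withdrawal the bias can match or exceed this. Recruiting replacements narrows the interval but leaves w × (p_c − p_w) unchanged.

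**The case against.** A reader might infer that nothing is collected at withdrawal. The documents contradict that: sections 5.5 and 14.2.1 call for a reason to be noted, and section 11.4.1 records adverse effects. Reasons are therefore sought. Even so, a reason that may be withheld, and that no section ties to acceptability, does not replace the questionnaire.

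A reader might also infer that anyone who stops a night is a withdrawal, or that only people who tolerated the EEG will ever answer. Neither is established. Section 9.5 foresees lost nights within continued participation, and section 6.3 v) sets no completion condition. The clear gap is for people who refuse at set-up, and it is probable for those who formally leave early. The Appendix 2 items do not settle the matter, since most could be answered by someone who stopped.

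Other points have some force. The count of missing EEG nights in 10.2 a) may pick up part of the intolerance, but it measures feasibility and does not say what people found unacceptable. The denominator for acceptability can properly be left to an analysis plan. Who is asked cannot, because later analysis does not recover answers never sought or data already discarded. The content of the section 7.1 timeline was not available in the text at hand, so it may show something the prose does not. Finally, all Appendix 2 items are free text, so the Protocol defines no percentage favourable and the figures above only indicate scale.

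**Conclusion.** The concern stands in a limited form. The Protocol records a non-mandatory withdrawal reason, but it does not offer the acceptability questionnaire to those who refuse the cap or leave early. It replaces them, and it permits some of their data to be discarded. A result for a listed primary objective may therefore rest mainly on people who tolerated the device.

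The size is unknown. Under the assumptions shown it is about 4-18 points at 10-20% withdrawal and 2-4.5 points at 5%, so it would be small if few people leave. Low withdrawal should not be presumed, since section 6.3 says the team has no current experience of sleep recordings in Alzheimer's disease. This should be corrected, but it does not invalidate the study.

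**What to change.** - **Sections 6.3 v), 5.5 and 8.2:** state that the Appendix 2 questionnaire is offered, as an option, to every eligible Sub-study 1 participant who is offered EEG. This includes anyone who declines or stops, at that contact or by telephone within 1 week. The group should not be everyone who consents: under section 5.3 consent precedes the MoCA, and people withdrawn on that score never meet the cap.
- **Reporting:** give acceptability over all participants offered EEG, including those later replaced. Show recorded stopping reasons and non-responders separately, subject to consent to use the data.
- **Section 11.4.1:** reconcile with 5.5, so that stopping because of the EEG is not a ground for discarding feasibility or acceptability data the participant agrees to keep.

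The cost is Protocol wording and one optional contact per early stopper. A researcher already visits each night and is available by telephone (section 6.4.1). Some people will decline, and that number is then reported. Because the offer is optional, the right to withdraw without explanation is unaffected.
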